3 INTRODUCTION

Ozanimod (RPC1063, BMS-986374) is a sphingosine 1-phosphate (S1P) receptor modulator that has been approved in the US, Europe, and other countries for the treatment of ulcerative colitis (UC) and multiple sclerosis (MS). The US Food and Drug Administration (FDA) approval of ozanimod (trade name Zeposia[®]) for the treatment of moderate to severely active UC was received in May 2021 and was based on data from the pivotal Phase 3 True North study (RPC01-3101) and supported by data from the Phase 2 Touchstone Study (RPC01-202), which evaluated ozanimod as an induction and maintenance therapy vs placebo in adult patients with moderate to severe UC.^{1,2}

3.1 Study Rationale

This prospective, open-label, Phase 4 study is designed to explore the safety, efficacy, effects on quality of life (QOL), and biomarker response of ozanimod in participants with moderate to severely active UC in clinical practice.

The study population will be consistent with the product label, so that this study may generate data that are directly relevant to the labeled indication and that may be used to further inform the clinical use of ozanimod in this study population.

The study will include 2 cohorts:

- **Cohort 1:** Participants with moderate to severely active UC who have not been exposed to biologics or immunomodulators for the treatment of UC (ie, advanced therapy-naïve).
- **Cohort 2:** Participants with moderate to severely active UC who have been exposed to a single mechanism of action of biologics for the treatment of UC (ie, advanced therapy-exposed).

This study will generate additional data on the effect of ozanimod treatment, including (but not limited to) the following:

- Characterization of early response (improvement in signs and symptoms of UC within the first 4 weeks), including rectal bleeding (RB), stool frequency (SF), urgency, and abdominal symptoms.
- Characterization of the endoscopic and histologic response to ozanimod at Week 12 in an advanced therapy-naïve cohort.
- Characterization of the endoscopic and histologic response to ozanimod at Week 26 in an advanced therapy-exposed cohort.
- Characterization of the long-term safety of ozanimod over the duration of the study.
- Patient-reported outcome (PRO) measures, including impact on disease-specific QOL and symptoms, fatigue, patient satisfaction with treatment, and work productivity.
- Characterization of the effect of ozanimod treatment on biomarkers of disease activity used in clinical practice, [REDACTED]

3.2 Background

3.2.1 *Ulcerative Colitis*

UC is a chronic gastrointestinal (GI) inflammatory disorder that involves the surface mucosa, the crypt epithelium, and the submucosa of the colon.^{3,4} The etiology of UC is multifactorial, but likely includes a dysregulated mucosal immune response against commensal nonpathogenic bacteria of the colon, resulting in bowel inflammation.⁵

Patients with UC suffer from diarrhea, RB, weight loss, abdominal pain, and fever.^{3,4} The pathology of UC is characterized by a life-long chronic course of exacerbations and remissions. In the case of severe UC, the bowel wall may become thinned, the mucosa denuded, and the inflammation may extend to the serosa, leading to dilation, toxic megacolon, and perforation.⁶ Toxic megacolon, although uncommon, may require an urgent colectomy to avoid perforation, peritonitis, and sepsis. Within 10 years of diagnosis, 19.9% of patients with UC have undergone colectomy.⁷

In addition, patients with UC have an increased risk of carcinoma when compared with the general population. The estimated risk of colorectal carcinoma increases as the duration and extent of disease increases, from 2% in patients with UC for 10 years, to 8% in patients with UC for 20 years, and to 18% in patients with UC for 30 years.^{8,9}

The overall goal of treatment for patients with active UC is to induce and maintain both remission and mucosal healing.¹⁰ Treatment of UC consists of anti-inflammatory and immunosuppressive therapies that are chosen to maximize efficacy while minimizing toxicity. The therapy chosen is therefore dependent on the patient's disease severity and their response to therapy.^{10,11} Although agents used to treat mild to moderate UC are generally well -tolerated, as the severity of UC disease increases, so too do the potential toxicities related to the medications required to manage the disease. Treatment for mild to moderate UC typically starts with topical agents (5-aminosalicylate [5-ASA] or corticosteroids administered via suppository or enema). In patients unresponsive to local therapy or in those with more severe or more extensive disease, oral 5-ASA, such as mesalamine, olsalazine, sulfasalazine, and balsalazide, with or without antibiotics, is commonly required.^{10,12} Initially, up to 90% of patients with mild to moderate UC can maintain their remission status using oral administration of 5-ASA, which is generally safe and well -tolerated.¹⁰

For those patients who do not respond or lose response to treatment with 5-ASA or for those with more severe and extensive disease at presentation, corticosteroids are generally the first-line treatment for inducing disease remission. Although effective in inducing disease remission, treatment with corticosteroids is associated with multiple adverse effects, including weight gain, insomnia, mood swings, osteoporosis, scalp hair loss or facial hair growth, moon face, cataracts, acne, hypertension, diabetes, appearance of stretch marks, and increased susceptibility to infections and bruising.

For those patients who are unresponsive to, or intolerant of corticosteroids, immunomodulators, including azathioprine (AZA), 6-mercaptopurine, and cyclosporine¹² are used to induce and/or

maintain remission.¹¹ However, these medications have multiple limitations, including toxicities. The use of 6-mercaptopurine and AZA can result in neutropenia, pancytopenia, pancreatitis, nephrotoxicity, hepatotoxicity, and, in rare cases, Epstein–Barr virus (EBV) and non-EBV-associated lymphoma, as well as the uniformly fatal hepatosplenic T cell lymphoma.^{13,14,15} A Cochrane systematic review concluded that available medical trials do not support the use of methotrexate for short- or long-term remission of active UC.¹⁶

Updated guidance on treating UC in adult patients emphasizes the role of biologic agents, including infliximab, adalimumab, golimumab (anti-tumor necrosis factor [TNF] therapies), vedolizumab (anti-integrin antibody), tofacitinib (Janus kinase [JAK] inhibitor), and ustekinumab (anti-interleukin [IL]-12/23 antibody).^{17,18} However, up to one-fifth of patients receiving anti-TNF agents may not demonstrate an initial response,¹⁷ and an additional 10% to 20% may lose response every year despite an initial benefit.^{19,20} The anti-TNF agents also come with the potential risk of infusion reactions or injection site reactions, infections, malignancy, autoimmunity, and psoriasis known for that medication class. Although tofacitinib is administered orally, the US FDA has approved new warnings on an increased risk of blood clots and death with the dose of tofacitinib that is used in patients with UC.²¹ Therefore, there remains an unmet need for a UC treatment that is effective, well-tolerated, and orally active. In this scenario, the US FDA approval of ozanimod, a selective S1P receptor modulator, as once daily (QD) per oral (PO) treatment in adults with moderate to severely active UC could help to fill a treatment gap in this disease.

3.2.2 Ozanimod

Ozanimod is a small molecule compound that selectively binds with high affinity to S1P receptors 1 and 5. In vitro, ozanimod has little activity on the other S1P receptors, showing half-maximal EC₅₀ > 10,000 nM for S1P2, > 5000 nM for S1P3, and > 2000 nM for S1P4.

Many cell types express S1P1, including vascular endothelial cells, brain cells, and lymphocytes. Stimulation (agonism) of this receptor results in biological activities that include lymphocyte retention in peripheral lymphoid organs (eg, lymph nodes and GI Peyer's patches), which can result in reversible systemic reduction in circulating lymphocytes.²² Given the immune-mediated inflammation in UC, prevention of circulation of disease-exacerbating, self-reactive lymphocytes to the gut is likely to have salutary immunomodulatory effects with a consequent dampening of disease processes.

An open-label, pharmacokinetic (PK)/pharmacodynamic (PD) study in patients with MS examined the effect of ozanimod on circulating leukocyte subsets.²³ Ozanimod 0.92 mg demonstrated greater reduction in CD4+ (helper) T cells than CD8+ (cytotoxic) T cells. Additionally, CD4+ and CD8+ central memory T cells were reduced more than CD4+ and CD8+ effector memory T cells, respectively. There was minimal impact on monocytes and natural killer cells. It was hypothesized that the differential impact on leukocyte subpopulations may provide inhibition of inflammation that may lead to pathophysiology in MS, while allowing for maintenance of immune function.

Leukocyte subpopulations in patients with UC who have received ozanimod have not yet been studied.

Ozanimod is extensively metabolized in humans to form a number of circulating active metabolites, including 2 major active metabolites (CC112273 [also referred to as RP112273] and CC1084037 [also referred to as RP100798]); other active metabolites, including RP101988, RP101075, RP112289, and RP101442; and one circulating inactive metabolite, RP101124. Ozanimod and its active metabolites have similar chemical structures, activity, and selectivity for S1P1 and S1P5 receptors. Following multiple -dose administration of ozanimod in healthy subjects, approximately 94% of circulating total active drug exposure was represented by ozanimod (6%), CC112273 (73%), and CC1084037 (15%).

3.2.3 Ozanimod in UC

In the True North study, a total of 645 participants were randomly assigned 2:1 to either ozanimod 0.92 mg QD PO (n = 429) or placebo (n = 216). The primary induction endpoint of clinical remission at Week 10 (18% vs 6%; P<0.0001, for ozanimod vs placebo, respectively) was met, as were the key secondary endpoints, including clinical response (48% vs 26%; P<0.0001), endoscopic improvement (27% vs 12%; P<0.0001), and endoscopic-histologic mucosal improvement (13% vs 4%; P<0.001). Decreases in RB and SF subscores were observed as early as Week 2 (ie, one week after participants completed the required 7-day dosage titration) in participants treated with ozanimod.

A total of 457 participants who received ozanimod in the induction period or in an open-label arm and achieved clinical response at Week 10 were re-randomized 1:1 and were treated with either ozanimod 0.92 mg QD PO (n = 230) or placebo (n = 227) for 42 weeks, for a total of 52 weeks of treatment. The primary endpoint of clinical remission at Week 52 was met (37% vs 19%; P<0.0001), as were the key secondary endpoints, including clinical response (60% vs 41%; P<0.0001), endoscopic improvement (46% vs 26%; P<0.001), corticosteroid-free clinical remission (32% vs 17%; P<0.001), and endoscopic-histologic mucosal improvement (30% vs 14%; P<0.001).

The safety and tolerability results from the induction and maintenance periods of the True North study demonstrated that ozanimod at a dose of 0.92 mg daily for 8 weeks or for 52 weeks, respectively, was well-tolerated and had an acceptable safety profile in patients with moderate to severely active UC. There was no evidence of new patterns of treatment-emergent adverse events (TEAEs), increased incidence of TEAEs, or unique TEAEs with longer exposure to ozanimod. Overall, these results were consistent with safety findings that have previously been reported regarding ozanimod therapy in Phase 3 trials involving patients with MS.

A detailed description of the efficacy and safety of ozanimod is provided in the product label.

3.3 Benefit/Risk Assessment

More detailed information about the known and expected benefits and risks and reasonably anticipated adverse events (AEs) of ozanimod may be found in the product label.

3.3.1 Risk Assessment**Table 3.3.1-1: Risk Assessment**

Potential Risk of Clinical Significance	Summary of Data/ Rationale for Risk	Mitigation Strategy
Study Intervention(s)		
Infections (eg, herpes viral infection, cryptococcal infection, PML)	Per Zeposia product label	Per Zeposia product label
Prior and concomitant treatment with anti-neoplastic, immunosuppressive, or immune-modulating therapies	Per Zeposia product label	Per Zeposia product label
Vaccinations	Per Zeposia product label	Per Zeposia product label
Bradyarrhythmia and AV conduction delays	Per Zeposia product label	Per Zeposia product label
Liver injury	Per Zeposia product label	Per Zeposia product label
Fetal risk	Per Zeposia product label	Per Zeposia product label
Increased blood pressure	Per Zeposia product label	Per Zeposia product label
Respiratory effects	Per Zeposia product label	Per Zeposia product label
Macular edema (eg, in patients with a history of uveitis or diabetes mellitus)	Per Zeposia product label	Per Zeposia product label
Posterior reversible encephalopathy syndrome	Per Zeposia product label	Per Zeposia product label
Unintended additive immunosuppressive effects from prior treatment with immunosuppressive or immune-modulating drugs	Per Zeposia product label	Per Zeposia product label
Immune system effects after stopping ozanimod	Per Zeposia product label	Per Zeposia product label
Study Procedures		
Endoscopy and biopsies	While endoscopy is considered to be a very safe procedure, rare complications may include perforation, bleeding, and infection. Risk of bleeding complications after an endoscopy is increased if the procedure involves biopsy	Per institutional protocol/investigator discretion
Other (if Applicable)		
SARS-CoV-2 infection	Current ongoing pandemic	Vaccination prior to enrollment is encouraged. The risk of enrolling participants with active SARS-CoV-2 infection will be minimized by testing at screening. General risk mitigation against SARS-CoV-2

Table 3.3.1-1: Risk Assessment

Potential Risk of Clinical Significance	Summary of Data/ Rationale for Risk	Mitigation Strategy
		infection will be implemented in accordance with the site's monitoring and prevention control measures. [REDACTED]

AV, atrioventricular; PML, progressive multifocal leukoencephalopathy; SARS-CoV-2, severe acute respiratory syndrome coronavirus 2

3.3.2 Benefit Assessment

Ozanimod has been approved in the US, Europe, and other countries for the treatment of moderate to severely active UC. Data from the Phase 3 True North study suggests that ozanimod is efficacious in the treatment of moderate to severe UC, with an acceptable safety profile. In the True North study, a significantly greater proportion of patients who received ozanimod achieved the primary induction endpoint (ie, clinical remission) as well as key secondary endpoints (ie, clinical response, endoscopic improvement, and endoscopic-histologic mucosal improvement) compared with those who received placebo. Longer exposure to ozanimod did not lead to any new safety concerns.

As this is an open-label study, participants are not at risk of receiving placebo, and ozanimod therapy is expected to potentially induce clinical remission, endoscopic response and improvement, histological improvement, and health-related quality of life (HRQOL) in this target patient population.

3.3.3 Overall Benefit/Risk Conclusion

Taking into account the measures taken to minimize risk to participants in this study, the potential risks identified in association with ozanimod are justified by the anticipated benefits that may be afforded to participants with moderate to severe UC.

The Sponsor will evaluate the risk/benefit profile of the study on an ongoing basis. This evaluation will be based on all available data with particular attention to i) AEs or other safety trends in this or any other clinical study of ozanimod whose character, severity, and/or frequency suggest that participants would be exposed to an unreasonable and significant risk of illness or injury; (ii) new nonclinical data suggesting unreasonable and significant risk of illness or injury.

If such evaluation suggests that the risk/benefit profile of the study has become unfavorable to participants, the Sponsor will pause enrollment and/or treatment until further evaluation of data can take place on potential actions. Such actions may include (but are not limited to) study continuation, substantial amendment, or termination of the study.

4 OBJECTIVES AND ENDPOINTS

The study objectives and endpoints are listed in the following 3 tables:

- Table 4-1: Objectives and endpoints that are specific to Cohort 1.
- [Table 4-2](#): Objectives and endpoints that are specific to Cohort 2.
- [Table 4-3](#): Objectives and endpoints that are common for both Cohort 1 and Cohort 2.

Additional endpoints and analyses will be described in the statistical analysis plan (SAP), the Endoscopy Image Review Charter, and/or the Histopathology Image Review Charter (as applicable). Selected endpoint definitions are provided in [APPENDIX 6](#).

Table 4-1: Objectives and Endpoints Specific to Advanced Therapy-naïve Cohort (Cohort 1)

Objectives	Endpoints
Primary 
• To explore the efficacy of ozanimod in inducing clinical response in the advanced therapy-naïve cohort.	Primary 
• Clinical response at Week 12, as measured by modified Mayo score.
Secondary 
• To explore the efficacy of ozanimod in the advanced therapy-naïve cohort.• To explore the effects of ozanimod on disease-specific HRQOL in the advanced therapy-naïve cohort.	Secondary 
• Clinical remission at Week 12, as measured by modified Mayo score.• Endoscopic response at Week 12.• Endoscopic improvement at Week 12.• Histological improvement at Week 12.• Change in the IBDQ total score from baseline to Week 12.• IBDQ response (change in total score [≥ 16 points] from baseline to Week 12).• IBDQ remission (total score [≥ 170 points]) at Week 12.

IBDQ, Inflammatory Bowel Disease Questionnaire.

Table 4-2: Objectives and Endpoints Specific to Advanced Therapy-exposed Cohort (Cohort 2)

Objectives	Endpoints
Primary 
To explore the efficacy of ozanimod in inducing clinical response in the advanced therapy-exposed cohort.	Primary 
Clinical response at Week 26, as measured by modified Mayo score.
Secondary 
To explore the efficacy of ozanimod in the advanced therapy-exposed cohort.	Secondary 
Clinical remission at Week 26, as measured by modified Mayo score.Endoscopic response at Week 26.Endoscopic improvement at Week 26.Endoscopic remission at Week 26.Histological improvement at Week 26.Histological remission at Week 26.Change in the IBDQ total score from baseline to Week 26.IBDQ response (change in total score [\geq 16 points] from baseline to Week 26).IBDQ remission (total score [\geq 170 points]) at Week 26.Corticosteroid-free clinical remission at Week 26, as measured by modified Mayo score.HEMI at Week 26.

HEMI, histo-endoscopic mucosal improvement; IBDQ, Inflammatory Bowel Disease Questionnaire.

Table 4-3: Additional Objectives and Endpoints Common for both the Advanced Therapy-naïve Cohort (Cohort 1) and the Advanced Therapy-exposed Cohort (Cohort 2) after Week 26

Objectives	Endpoints

Secondary
 
• To explore the safety and tolerability of ozanimod in the advanced therapy-naïve cohort and the advanced therapy-exposed cohort.• To explore the long-term durability of response to ozanimod in the advanced therapy-naïve cohort and the advanced therapy-exposed cohort.	
Secondary
 
• Number and proportion of participants experiencing the following:
– AEs.– SAEs.– AEs and SAEs, including AEIs and other select AEs, leading to discontinuation from the study intervention and the study.– Clinical laboratory values.• Clinical remission by partial Mayo score at Weeks 52 and 104.• Corticosteroid-free clinical remission by partial Mayo score at Weeks 52 and 104.• Clinical response by partial Mayo score at Weeks 52 and 104.

Table 4-3: Additional Objectives and Endpoints Common for both the Advanced Therapy-naïve Cohort (Cohort 1) and the Advanced Therapy-exposed Cohort (Cohort 2) after Week 26

Objectives	Endpoints
AEI, adverse event of interest;	SAE, serious adverse event;

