7.7.2.1 Treatment Failure Rules

Treatment failure rules will be applied to the primary analyses of all efficacy endpoints. Participants will be considered to have failed treatment if any of the following occur:

- Any protocol-prohibited change in medications, including:
 - Post-baseline initiation of or increase in total daily dose to a level higher than the 40 mg maximum permitted dose of corticosteroid to treat UC.
 - Prolonged course of systemic corticosteroids (ie, > 12 consecutive weeks) for treatment of UC.
 - Initiation of an immune-suppressing therapy, including 6-mercaptopurine, AZA, methotrexate, anti-TNF agents, anti-integrin, anti-IL-12/23 agents, or JAK inhibitors.
- A colectomy (partial or total) or an ostomy.
- Discontinuation of the study intervention due to lack of therapeutic effect before primary or secondary efficacy evaluations.

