10.3 Analysis Sets

For the purposes of analysis, the populations are defined as follows:

Population	Description
Enrolled	All participants who signed an ICF and were registered into IRT.
Cohort 1 Treated Analysis Population	All Cohort 1 participants who received at least one dose of study intervention. This population will be used for both the efficacy and safety analyses for Cohort 1.
Cohort 2 Treated Analysis Population	All Cohort 2 participants who received at least one dose of study intervention. This population will be used for both the efficacy and safety analyses for Cohort 2.
Defined Analysis Data Sets	Description
Analysis set for primary estimand (Cohort 1)	All Cohort 1-treated participants. Participants who discontinued study intervention and/or received prohibited concomitant medications prior to Week 12 will be considered non-responders.
Analysis set for primary estimand (Cohort 2)	All Cohort 2-treated participants. Participants who discontinued study intervention and/or received prohibited concomitant medications prior to Week 26 will be considered non-responders.

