10.4.3 Primary Endpoint

The primary endpoint for each cohort, their corresponding descriptions, and prespecified time points are listed in Table 10.4.3-1.

The primary endpoint for Cohort 1 is the proportion of participants who achieve a clinical response at Week 12. The clinical response rate at Week 12 will be estimated, and the corresponding 95% CI will be derived based on the Clopper Pearson method.

The primary endpoint for Cohort 2 is the proportion of participants who achieve a clinical response at Week 26. An estimate of the clinical response rate at Week 26 will be provided, along with the corresponding 95% CI derived based on the Clopper Pearson method.

For proportion-based efficacy endpoints, patients with missing Week 12 efficacy data from Cohort 1 and/or participants with missing Week 26 efficacy data from Cohort 2 will be considered non-responders, and non-responder imputation will be used. Sensitivity analyses around missing data may involve missing data imputed using multiple imputation and may analyze observed cases with no imputation. Details of the sensitivity analysis will be provided in the SAP.

For continuous efficacy endpoints, observed cases will be analyzed with no imputation.

Table 10.4.3-1: Endpoints

Primary	Description	Timeframe
Clinical Response (modified Mayo score)	Proportion of participants achieving the following: 
Decrease from baseline in the modified Mayo score of ≥ 2 points, andDecrease from baseline in the modified Mayo score of $\geq 35\%$, andDecrease in RB subscore of ≥ 1 point or absolute RB subscore ≤ 1.	Week 12 (Cohort 1) Week 26 (Cohort 2)
Secondary	Description	Timeframe
Clinical Remission (modified Mayo score)	Proportion of treated participants achieving the following in each component of the modified Mayo score: 
SF subscore ≤ 1, with ≥ 1-point decrease from baseline, andRB subscore = 0, andES ≤ 1.	Week 12 (Cohort 1) Week 26 (Cohort 2)
Endoscopic Response	Proportion of treated participants with a decrease from baseline of ≥ 1 point in Mayo ES	Week 12 (Cohort 1) Week 26 (Cohort 2)
Endoscopic Improvement	Proportion of treated participants with Mayo ES ≤ 1	Week 12 (Cohort 1) Week 26 (Cohort 2)

Table 10.4.3-1: Endpoints

Endoscopic Remission	Proportion of treated participants with Mayo ES = 0	Week 26 (Cohort 2)
IBDQ Response	Proportion of participants with a change from baseline in total score of ≥ 16 points	Week 12 (Cohort 1)

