10.4.4 Secondary Endpoints

All secondary endpoints, their corresponding descriptions, and prespecified time points are listed in [Table 10.4.3-1](#) for each cohort.

For all binary response secondary endpoints in each cohort, the response rate at the prespecified time point will be estimated and a corresponding 95% CI will be derived based on the Clopper Pearson method. Details of the analysis for each secondary endpoint will be specified in the SAP.

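### In the readable text, long-term durability of response is addressed only by all-treated Week 52 and Week 104 partial Mayo rates, which do not show what fraction of early responders were still in response

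*Combined protocol and SAP*

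**What the plan says.** **Objective and endpoints.** Table 4-3 gives the durability objective for both cohorts: "To explore the long-term durability of response to ozanimod". Its readable efficacy endpoints are partial Mayo clinical remission, the corticosteroid-free version of that remission, and "Clinical response by partial Mayo score at Weeks 52 and 104". None is restricted to participants who had responded earlier.

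**Denominator.** Section 10.3 defines a treated population for each cohort. For Cohort 1 it states "This population will be used for both the efficacy and safety analyses for Cohort 1", and it says the same for Cohort 2. It defines no responder subset. Section 10.4.4 plans a rate with a Clopper-Pearson interval at each time point.

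**Definitions.** Appendix 6 defines partial Mayo remission but not partial Mayo response. Section 10.4.4 says "All secondary endpoints, their corresponding descriptions, and prespecified time points are listed in" Table 10.4.3-1, but that table has no Week 52 or Week 104 row. The same section adds: "Details of the analysis for each secondary endpoint will be specified in the SAP".

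**Failures and missing data.** Section 7.7.2.1 states "Treatment failure rules will be applied to the primary analyses of all efficacy endpoints". It counts prohibited medication changes, colectomy or ostomy, and stopping for lack of effect. The wider rules name only the primary visits. Section 10.3 treats any discontinuation before Week 12 (Cohort 1) or Week 26 (Cohort 2) as non-response. Section 10.4.3 covers missing data at those same visits, for example "participants with missing Week 26 efficacy data from Cohort 2 will be considered non-responders".

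**Deferral.** Section 4 leaves additional endpoints and analyses to the SAP. No separate SAP text is in the document reviewed.

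**The concern.** Durability of response asks what became of those who responded. A rate among all treated participants at Week 52 counts everyone in response at that visit, whether they responded early and kept it or responded only later. The same rate can therefore come from good maintenance with few late responders, or from poor maintenance with many.

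Comparing the early and late rates does not solve this. The early endpoint uses the modified Mayo score, which includes endoscopy. The late endpoint uses the partial Mayo score, which replaces endoscopy with the physician's global assessment (Appendix 3).

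At stake is the interpretation of one secondary objective. The primary analyses and the sample size are not affected.

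**Working it through.** **1. The plan's own figures.** Clopper-Pearson 95% limits for x of n are the 2.5% quantile of Beta(x, n−x+1) and the 97.5% quantile of Beta(x+1, n−x). For Cohort 1, 75/150 gives 41.7% to 58.3%, as in Section 10.2. For Cohort 2, 45/100 gives 35.0% to 55.3%, also as stated.

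**2. Inputs.**
- Treated: N = 150 and 100 (Section 10.2).
- Early responders: R = 50% × 150 = 75 in Cohort 1, and 35% to 45% × 100 = 35 to 45 in Cohort 2 (Section 10.2). These are modified Mayo planning rates. The documents give none for partial Mayo response, so using them here is an assumption.
- Responders at Week 52: L = 60 of 150 and 36 of 100. Both are assumed, since no planning value is given.

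**3. What the all-treated rates allow.** The number in response at both visits lies between max(0, R + L − N) and min(R, L). Dividing by R bounds the retained fraction.
- Cohort 1: 75 + 60 − 150 = −15, so the lower bound is 0. The upper bound is 60/75 = 80%.
- Cohort 2, with R = 45: 45 + 36 − 100 = −19, so the lower bound is 0. The upper bound is 36/45 = 80%.
- If Cohort 1 had 75 of 150 in response at both visits, the bounds would be 0% to 100%.

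Less extreme splits of the same Week 52 totals:

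| Cohort | Late responders among early non-responders | Early responders in response | Fraction |
|---|---|---|---|
| 1 (60 at Week 52) | 0 of 75 | 60 of 75 | 80% |
| 1 | 6 of 75 | 54 of 75 | 72% |
| 1 | 15 of 75 | 45 of 75 | 60% |
| 2 (36 at Week 52) | 0 of 55 | 36 of 45 | 80% |
| 2 | 4 of 55 | 32 of 45 | 71% |
| 2 | 11 of 55 | 25 of 45 | 56% |

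**4. Precision of a responder-based rate.** I take 60% retained as an illustration. It equals the Week 52 response rate in Section 3.2.3 for Week 10 responders re-randomized to ozanimod in the pivotal study. The protocol does not use it as a benchmark.

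| Cohort | In response / early responders | 95% CI | Half-width (points) |
|---|---|---|---|
| 1 | 36/60 | 46.5% to 72.4% | 12.9 |
| 1 | 45/75 | 48.0% to 71.1% | 11.6 |
| 1 | 54/90 | 49.1% to 70.2% | 10.5 |
| 2 | 15/25 | 38.7% to 78.9% | 20.1 |
| 2 | 21/35 | 42.1% to 76.1% | 17.0 |
| 2 | 27/45 | 44.3% to 74.3% | 15.0 |
| 2 | 33/55 | 45.9% to 73.0% | 13.5 |

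Only the denominators 75, 35 and 45 match planning rates. For comparison, an all-treated rate of 40% gives 32.1% to 48.3% (60/150, ±8.1) and 30.3% to 50.3% (40/100, ±10.0).

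**5. Data and follow-up.** Tables 2-1 and 2-2 schedule stool frequency, rectal bleeding and the physician's global assessment at Day 1 and Weeks 12, 26, 52 and 104. From the anchor visit, follow-up to Week 52 is 52 − 12 = 40 weeks in Cohort 1 and 52 − 26 = 26 weeks in Cohort 2. To Week 104 it is 92 and 78 weeks.

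**The case against.** **The text is incomplete.** The continuation page of Table 4-3 has no readable rows, the heading between Sections 10.4.4 and 10.4.6 is redacted, and so are parts of 10.4.7. The SAP may also add endpoints. A reader might infer that the trial has no responder-based durability analysis. The documents do not support that, and the point is confined to what can be read.

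**Deferral is deliberate.** Section 10.4 requires the SAP before database lock, while Section 10.5 allows an analysis once all participants reach Week 52. A reader might infer that definitions would be chosen after that look. Nothing shows this: Section 10.5 calls the analysis pre-planned, and the protocol summary says the SAP will describe the interim analyses. Fixing definitions first is a precaution in an open-label study. The undefined response and the absent table rows are mostly deferred detail. Table 10.4.3-1 also omits the histological endpoints and IBDQ change, so the omission is not peculiar to durability.

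**All-treated rates are defensible.** The objective is exploratory, no hypothesis is tested, and these rates avoid selecting on a post-baseline outcome. This stands, and they should stay.

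**A responder-based rate has its own limits.** After Week 12 the diary covers only the 7 days before each visit, and no visit is scheduled between Weeks 52 and 104. Loss and regain between visits would go unseen. Table 7.7-3 permits steroid courses that Section 7.7.2.1 does not count as failure, so response at a visit may be steroid-supported. Partial Mayo responders are also not the same group as the primary-endpoint responders. These limits stand and shape the fix.

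**Conclusion.** The point holds for the readable text. The Week 52 and Week 104 rates are sound long-term summaries, but they do not identify the fraction of early responders still in response. With the illustrative counts, that fraction could be anywhere from 0% to 80% in either cohort. This shows what the rates leave open; it does not estimate a likely error. It rests on assumed Week 52 counts and on modified Mayo planning rates standing in for partial Mayo rates.

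Two stronger readings should be set aside. Late failures are not wholly unhandled, because Section 7.7.2.1 applies to all efficacy endpoints; the gap is in missing data and other discontinuations at Weeks 52 and 104, and no size is claimed for it. Nor would the added analysis prove continuous maintenance: it gives response status at scheduled visits.

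This is an inexpensive improvement worth making to a secondary objective.

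**What to change.** **Add to the existing endpoints, per cohort, with Clopper-Pearson intervals:**
- The proportion of Week 12 (Cohort 1) or Week 26 (Cohort 2) partial Mayo responders who are in partial Mayo response at Week 52, and at both Weeks 52 and 104.
- For Cohort 1, also the proportion in response at Weeks 26 and 52, and at Weeks 26, 52 and 104.
- The same table anchored on the primary-endpoint (modified Mayo) responders.
- A corticosteroid-free version using the rule in Appendix 6, which looks back 90 days for oral systemic steroids. Apply it at the later visits: Week 12 is Day 84, so a 90-day look-back from there would reach before Day 1.

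Describe the results as response status at scheduled visits, and state that the cohorts are not comparable because follow-up from the anchor visit to Week 52 is 40 versus 26 weeks.

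**Settle first, before the Week 52 data cut:**
- Define partial Mayo response, for example by applying the Appendix 6 response criteria to the partial Mayo score, and add the Week 52/104 rows to Table 10.4.3-1.
- Extend non-responder handling to missing data and other discontinuations at Weeks 52 and 104, with observed cases as sensitivity.

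**Cost.** Wording and a few tables, with no new assessments. Section 4 lets the SAP carry this. Under Section 10.4 an amendment is needed only if it counts as a major modification of key endpoint definitions or their analyses. The price is wider intervals than the all-treated rates give, and a subset selected after baseline, so the rates are descriptive only. Non-responder handling will give rates no higher than observed cases, and lower wherever data are missing.
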